Adverse Event Monitoring. Participants who miss sessions will be contacted by their coach. If the coach is informed that the participant is hospitalized or deceased, the coach will report that information to AECOM or PCIP/NYC-DOHMH project manager immediately, who will in-turn report it to [name]. The two follow-up surveys (after completion of 16 Core sessions, and after completion of 6 maintenance sessions) also include questions about hospitalizations and other serious adverse events. These surveys will be administered primarily by telephone by our research staff based at our two sites and occasionally in person, when meeting participants to collect missing weights who have also been non-responsive to attempts to schedule a telephone survey, using equivalent procedures to those used for telephone administration. If, 1) the interviewer is informed of an adverse event in the course of the survey, or 2) while trying to reach the participant, the interviewer is informed by someone in the household of a subject's hospitalization or death, that event will be noted. Any hospital admission for a related condition or death from any cause will be immediately reported to [name] who will record them. The Einstein IRB will maintain reports of adverse events.

Information about adverse events will be sought as described above. Unanticipated (non-serious) adverse events will be reported to the IRB within 30 days of such an event using the AECOM IRB Adverse Event Report. Serious adverse events will be reported to the IRB within 48 hours by phone and email. A completed AECOM IRB Adverse Event Report will be submitted within 10 days of initial IRB notification. All deaths will be reported to the IRB within 48 hours of ascertainment. The monitor will maintain a file of all ascertained adverse events that can be used to submit summary reports.

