4. Make recommendations to the PIs about continuation, modification, or termination of the intervention based on adverse events or beneficial outcomes.
5. Request interim analyses.
6. Monitor the confidentiality of the intervention data and the results of monitoring.
7. Offer consultation to the investigators on procedures likely to increase participants' burden, to raise ethical concerns, or to give the appearance of conflict of interest.

The following data will be available to the DSMB Board:

1. All adverse events: We are required to report in writing adverse events to our IRB within 48 days from the time that we become aware of an adverse event. The adverse event forms will be made available to the DSMB as well as tables summarizing the occurrence of specific events; such tables can help identify the systematic occurrence of an adverse event and lead to protective measures. As we are already required to report each event to our IRB, we plan to report to DSMB these adverse events and updated summary tables within 48 hours from each adverse event.

2. Any analyses requested by the DSMB Board.

3. Manuscripts and publications.

The DSMB will convene at least once annually, and more often as needed, either in person if logistically feasible, or by phone/Zoom video conference. The meeting will begin with a progress report by the PIs, followed by a report on any adverse events from [name]. We will then discuss interim results on Reach (characteristics of those who participate vs. refuse), Representativeness; Adoption (percent of practices approached who agree to participate), and Implementation (consistency of study recruitment and assessment procedures, fidelity checklist ratings from coaches and fidelity ratings based on observation by Drs.

[name] and [name], any modifications to the protocol for implementation, etc). To preserve investigator blinding of outcomes that may bias their interpretation of data or approach to the protocol, interim data on Effectiveness will not be reviewed by the investigators or the DSMB, unless specifically requested by the DSMB due to safety concerns. The DSMB will conclude the meeting without the investigators present and will make a recommendation about continuation of the study.

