Early Termination. [name] and [name] will determine if the study is to be terminated prior to the scheduled study conclusion, in consultation with our DSMB. Early study termination will be considered in the event of a pattern of unanticipated serious adverse events determined to be possibly, probably or definitely related to the intervention or the data collection. In such a case, interim assessment would also be considered to ascertain if the events were associated with the intervention. In the absence of a pattern of unanticipated serious adverse events, given the minimal risk character of the intervention of this study, traditional statistical stopping rules for efficacy or safety of the intervention would not be applicable. However, early study termination will be considered if:

- subject recruitment falls below 20% of the projected number of subjects 6 months after the initiation of all stepped and potential recruitment strategies have been utilized, or
- if we fail to retain (as defined above) at least 70% of enrolled study subjects at any annual review.

[name] will consult with [name], come to agreement, seek consultation from the DSMB, and report a decision to terminate the study early to the IRBs within 48 hours of the determination and a narrative description of the reasons for early termination within 10 days.

Contact PD/PI: [name]

Overall Structure of the Study Team

The study team will be led by Drs. [name] and [name] (PIs), who are both based at Albert Einstein College of Medicine. Our AECOM study offices will house a project manager and two study coordinators who will have primary responsibility for conducting and overseeing all research activities related to participants recruitment and workshop. Drs. [name] and [name] (Co-Is) are also based at AECOM.

At PCIP/DOHMH [name] will oversee activities related to practice engagement, participant recruitment, assessment, and intervention delivery to participants recruited from PCIP-affiliated primary care practices. She will be supported by a full time onsite research assistant in our PCIP-based study office. She will coordinate regularly with the Einstein-based project manager and receive regular supervision from [name] to ensure consistency of procedures. Together, this team will provide input to the study plans and procedures from both Einstein and PCIP/DOHMH.

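### The immediate report of hospital admissions carries an undefined relatedness filter that the coach route and the all-events provisions do not, and no stated step takes the remaining survey-reported admissions to the monitor

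*Protocol*

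**What the plan says.** All the relevant text is in the protocol's Data and Safety Monitoring Plan.

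**Coach route (Adverse Event Monitoring).** "If the coach is informed that the participant is hospitalized or deceased, the coach will report that information to AECOM or PCIP/NYC-DOHMH project manager immediately". The project manager then informs a named person. Relatedness is not a condition.

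**Survey and household route (same paragraph).** The two follow-up surveys "also include questions about hospitalizations and other serious adverse events". An adverse event that comes up in a survey is to be noted. Likewise, if "the interviewer is informed by someone in the household of a subject's hospitalization or death, that event will be noted". No recipient is given at this step. The next sentence supplies one: "Any hospital admission for a related condition or death from any cause will be immediately reported to" a named person, who records them.

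**Downstream provisions.** "The monitor will maintain a file of all ascertained adverse events that can be used to submit summary reports". Serious adverse events go to the IRB within 48 hours. The list of data for the DSMB opens with all adverse events and promises the events and updated tables within 48 hours; the reason given is that "such tables can help identify the systematic occurrence of an adverse event and lead to protective measures".

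**Early Termination.** Stopping is considered on a "pattern of unanticipated serious adverse events determined to be possibly, probably or definitely related to the intervention or the data collection".

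**The concern.** The same admission is handled differently depending on who hears of it first. Told to a coach, it is passed on whatever its cause. Told to an interviewer, it has a stated onward path only if it is for a related condition. That phrase could mean related to prediabetes, to physical activity or to the intervention, and someone must decide before the named person is told.

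The order matters. A monitor or DSMB looking for an unexpected excess of admissions needs all of them, because an excess can consist of events that each look unrelated when taken singly. The Early Termination trigger already depends on a relatedness determination. If an unassigned and undefined sort comes before it, the determination may be made on incomplete material.

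**Working it through.** No arithmetic bears on this point, and the plan gives no figure to reproduce. The check is to follow one event, a hospital admission, along each route.

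1. **Is every admission meant to be captured?** Yes. The survey wording ("also include questions about hospitalizations and other serious adverse events") treats hospitalizations as one kind of serious adverse event, whatever the cause.

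2. **Which admissions does a coach pass on?** All that the coach hears of: "If the coach is informed that the participant is hospitalized or deceased, the coach will report that information". But this route starts from contact with men who miss sessions, so it is not a systematic inquiry.

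3. **Which admissions does an interviewer pass on?** All are noted. The only sentence that moves information from this point to a named person covers admissions for a related condition and deaths from any cause. The contrast within that sentence makes the restriction on admissions look intended.

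4. **Does the sentence apply to the survey route alone?** Its position, straight after the interviewer sentence, suggests so. If it covers both routes, it contradicts the coach sentence. The text needs reconciling on either reading.

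5. **Do the later provisions carry the condition?** No. The monitor's file, the 48-hour IRB report and the DSMB listing all have no relatedness condition. If hospitalizations are serious adverse events, as item 1 indicates, an unrelated admission noted at a survey is due at the IRB within 48 hours, yet no stated step brings it to anyone who would report it. (The DSMB list also gives a 48-day limit for written IRB reports. That is a separate inconsistency and is not relied on here.)

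6. **Is there another systematic source?** None is stated. The data to be extracted from health records are described as weights and clinical variables such as HbA1c, blood pressure and lipids; hospitalizations are not mentioned. The surveys are the only planned inquiry about admissions put to participants in both arms: 300 men × 2 follow-up surveys = at most 600 scheduled interviews.

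7. **Who judges relatedness, and when?** Neither the Adverse Event Monitoring paragraph nor the Early Termination paragraph says.

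The plan therefore promises complete reporting at the end and describes an incomplete path to it from its main source of information on admissions.

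**The case against.** The strongest reply is that the sentence governs timing and does not exclude anything. It says which admissions are reported immediately; it does not say that the others are withheld. An event noted at a survey has been ascertained, so it belongs in the monitor's file. The opening of the Data and Safety Monitoring Plan has all staff supply the monitor with the data needed after any adverse event, and section 2b, Protection Against Risk, provides for ongoing review of de-identified data. The DSMB may recommend termination on adverse events and may request interim analyses, in neither case subject to relatedness.

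Much of this stands, and it limits the point. A reader might infer that unrelated admissions never reach the monitor, the DSMB tables or the stopping decision. The documents do not support that: not being reported immediately is not the same as not being reported.

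A reader might also infer that survey staff, possibly aware of the arm, decide causality and would lean towards calling events unrelated. That is not supported either. No classifier is named, the verb is passive, and the phrase may mean a condition linked to prediabetes and not a causal link to the intervention. Section 1b does have study coordinators told the assignment, but it does not say that they sort admissions.

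The reply does not remove the gap. The general provisions state what the monitor and DSMB should hold. None says how or when a noted admission gets there, and the one specific step carries a filter.

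**Conclusion.** The point holds as a contradiction in the safety-reporting text. The immediate report of admissions is restricted by an undefined qualifier, assigned to nobody, that conflicts with the coach route and with the all-events provisions for the monitor, the IRB and the DSMB. As a result, admissions learned through surveys or household contacts may arrive late, incompletely or after an unassigned sort on relatedness.

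The size cannot be put in numbers. A count of affected admissions would need an admission rate and the share judged related. The protocol gives neither, and a count of lost events would also assume that what is not reported at once is never reported. The conclusion does not depend on such a count.

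Two assumptions remain. Names are removed from the text, so the person who receives the immediate report is taken to be the one responsible for safety monitoring. The qualified sentence is read as following on from the interviewer sentence; on the other reading the conflict with the coach sentence is direct.

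The protocol describes the trial as minimal risk and expects no attributable serious events. The change should be made because it is cheap and makes the safety data more complete, not because harm has been shown to go undetected.

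**What to change.** In Adverse Event Monitoring, delete the related-condition qualifier, so that every hospital admission and every death goes to the monitor by one route, whether a coach, a survey or a household contact is the source. State that events noted by an interviewer are forwarded on that route and entered in the monitor's file, from which the IRB and DSMB reports are drawn. State also that relatedness is assigned by the monitor after the report is received, and not by the interviewer, so that the determination on which Early Termination relies has a named owner and a complete set of events.

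The Early Termination trigger itself need not change to resolve this inconsistency.

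The cost is a few sentences of protocol text and some additional case reports for the monitor to log. No new data collection is needed, since the surveys already ask about hospitalizations.

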The proposed study builds on this successful NIDDK-funded pilot work to address the clear need for a men-tailored approach to diabetes prevention. *Power-Up* is an intervention that is: a) tailored to the needs and preferences of racial/ethnic minority men; b) delivered by men coaches in men-only groups; and c) uses adapted content that highlights issues relevant to men and messaging designed to be acceptable and engaging to men. Based on the pilot results, we propose to conduct a rigorous effectiveness evaluation using a pragmatic RCT design within diverse healthcare settings already implementing standard mixed-gender NDPP. The goals of this study are to: 1) test the effect of *Power-Up* on weight loss; 2) evaluate engagement of men in *Power-Up*; and 3) examine the reach, broader effectiveness, implementation, and costs of *Power-Up* to inform future dissemination efforts and plans for sustainability.

The proposed study will leverage existing collaborations with co-investigators testing best practices for recruitment, implementation and evaluation of NDPP in a bureau of the New York City Department of Health and Mental Hygiene. Through this partnership we will recruit 300 men from across a spectrum of primary care centers - from a major urban academic medical center to small- and medium-sized primary care practices throughout New York City serving disadvantaged communities. Electronic Health Record data will facilitate outreach to the population of eligible men, based on NDPP criteria, rather than relying on physician referral, and will establish a valid denominator for the total population of eligible men, allowing for a rigorous assessment of the reach of our recruitment approach and an evaluation of the representativeness of our sample. Indicators of effectiveness, adoption, implementation and cost will be analyzed, guided by the RE-AIM framework.

Aim 1. Assess the effect of *Power-Up* vs. NDPP on weight loss among racial/ethnic minority men at risk for diabetes.

Hypothesis 1 (Primary Outcome): Men randomized to *Power-Up* will achieve significantly greater weight loss at 16-weeks and 1-year than men in the standard care group referred to mixed-gender NDPP classes.

Aim 2. Compare engagement of racial/ethnic minority men at risk for diabetes in *Power-Up* vs. NDPP.

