We have planned our study to ensure sufficient time to recruit and follow-up our 300 participants before a 6-month period at the end of the study that will be concentrated on data analysis, writing-up of results, and dissemination. To achieve this goal, we will begin recruitment and implementation of the assessment and intervention procedures of the study at month 6 of the first year of funding. The first 6 months of the first year will be focused on hiring of staff, study-start-up, ordering of materials, setting-up databases for study variables, finalizing data extraction protocols, finalizing qualitative interviewing questions and procedures, and, finalizing procedures and intervention content in consultation with our expert Advisory Board. We have sufficient time to meet our study milestones and recruitment goals and plan time the cycles of intervention to ensure successful progress. The study will last 60 months, with start-up activities taking place in months 1-6. Intervention Cycles will run simultaneously between the 2 intervention settings over a 3-year period of the award. We will recruit 300, run 8 intervention cycles of approximately 40 men randomized 1:1 to each arm in months 13-54. Follow-up 16-week and 12-month assessments will be completed in months 24-54. Data analysis and dissemination activities will take place in months 55-60. Our budget allows us to hire 8 coaches in year 1 and up to another 8 coaches in year 3, ensuring our ability to run a sufficient number of groups.

Study Activity Timeline

Study Activity	Year 1		Year 2		Year 3		Year 4		Year 5	
Meetings with Advisory Board										x
Train coaches in implementation and data collection			x		x					
Recruitment data abstraction, mailings & outreach			x	x	x	x	x			
Baseline weight assessment and surveys			x	x	x	x	x			
Implement Power-Up sessions			x	x	x	x	x	x	x	
Observe Power-Up and DPP sessions for fidelity				x	x	x	x	x	x	
Practice Exit Interviews				x	x	x	x	x	x	
Follow-up weights and surveys (16 wks and 12 mos)				x	x	x	x	x	x	
Participant focus groups and individual interviews				x	x	x	x	x	x	
Lifestyle coach surveys				x	x	x	x	x	x	
Lifestyle coach interviews				x	x	x	x	x	x	
Analyses, publications, and reports for dissemination										x

Intervention Cycles Timeline

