Study procedures will primarily take place in our study offices at AECOM and PCIP/NYC-DOHMH and at local sites of participating practices from the PCIP and MMG networks. Additional procedures for weight collection, when participants do not attend intervention sessions where weights are primarily measured, may take place at additional sites. Recruitment, eligibility screening, and enrollment procedures will be conducted by research assistants/prevention outreach specialists located at our AECOM and PCIP/NYC-DOH offices. Potentially eligible men will be: via telephone follow-up; informed of their risk for diabetes and the availability and efficacy of the DPP; evaluated for eligibility; asked to provide oral informed consent by phone; and then randomized to one of the two conditions. Random assignment will be conducted using envelopes with the randomization condition inside. The research coordinator will have access to the envelopes. Study coordinators will contact the research coordinator who will tell the SC which condition the participant will be receiving. Randomization will occur at AECOM for all participants. Random assignment, and final enrollment into the study will occur after telephone screening, and completion of baseline surveys. With leadership from [name] (Co-I), all

coach training for *Power-Up* intervention delivery will occur in AECOM or PCIP/NYC-DOHMH meeting space. NDPP training for coaches will occur through established programs.

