
The primary outcome measure will be percent change in weight at the end of the Core (16 weekly) sessions and at the end of 12 months. We will examine several process and moderating variables, based on a telephone survey of self-report measures validated for English and Spanish language and in-person and telephonic administration, as well as EHR-extracted clinical variables, such as A1c, blood pressure, lipids, etc. 6 months after the delivery of the final session weights will also be EHR-extracted from clinical visits during the 1-year trial period, the 6 month wait is to allow for the updating of EHR data. Extracting these weights will help us capture weights for those who never attended sessions. Coaches will record , weight (using wireless internet connected scales), session attendance logs via study- ID coded and de-identified data entry. They will also complete fidelity checklists. Both of these data entry protocols will be supervised for quality control by study staff. Staff will also track and keep records of all study- related costs. These records will be reviewed periodically by the project managers of each site and by [name] (Co-I). Through coach surveys, coach interviews and participant individual interviews and focus groups, we will examine perceptions of *Power-Up*, fidelity to the model, barriers and facilitators to implementation and engagement, and recommendations for improvement. Participant identifying information will only be known to the primary study staff. Identifying information will be stored separately from study data in locked file cabinets in our study offices. Data will not be shared between study staff of participating health care systems and de-identified data for *Power-Up* participants will be shared with the *Power-Up* data analyst ([name], Co-I) for analysis.

Potential risks of participation are minimal and include the possibility that some participants may feel uncomfortable answering questions, or talking about their weight, food habits, physical activity, and factors that affect behavior. The intervention does not convey more than minimal risk and there is no reason to suspect that any serious adverse events will be attributable to it. All participants will be strongly encouraged to speak to their health care provider about safe and appropriate levels of exercise, as they would for any change in

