Potential participants who do not have capacity to provide consent will be provided with information about how to access the NDPP through talking with their provider who would discuss whether the program may or may not be appropriate for them. Potentially eligible subjects will be invited to participate, consented, randomized to a study arm and either directed to the *Power-Up* intervention coordinator or to the NDPP coordinator at PCIP depending on the patient's health care home. The consent document will include information about study procedures, including that participants will be randomized to either standard NDPP or *Power-Up*, that they will be contacted by telephone, email (if applicable) and mail for follow-up surveys, and the risks and benefits of the intervention. We will ask for permission to leave telephone messages, without identifying the exact purpose of the call, when we are making study-related calls. We will also ask for permission to send text messages via the coaches as reminders for sessions and questionnaires. Participation in the proposed study will be completely voluntary. Prospective subjects will be told that a decision to decline participation will not affect their health care.

The proposed research will follow the Health Insurance Portability and Accountability Act of 1996 (HIPAA) guidelines for protecting the privacy and documenting informed consent of participants. Intervention recruitment, consent, and enrollment will not begin until the study receives approval from the AECOM IRB, as outlined in the Consortium of Informed Consent Section.

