Recruitment Monitoring. Once initial recruitment begins, the study director will compile a weekly and cumulative tally using study identification numbers of recruited and randomized subjects. Drs. [name] and [name] and co-Is will assess on a bi-yearly basis the feasibility of reaching projected recruitment targets based on interim recruitment and retention reports. Regarding retention, all recruited participants will be included in the analyses on an intention-to-treat basis unless they request to be dropped from the study specifically. Participants 1) requesting only an end to the intervention, 2) who cannot be contacted or 3) for whom outcome measures are not available, will be included in the analysis for outcome measures that are available. These latter subjects will not be considered drop-outs for purposes of retention statistics.

Data Safety and Monitoring Board. [name] will have primary responsibility for ongoing monitoring of data related to safety for this study on an on-site, day-to-day basis. He will consult regularly with [name] on the results of his monitoring to discuss any concerns related to safety or the integrity of the study. However, because this is a Phase III Clinical Trial, we will also establish an independent Data Safety and Monitoring Board (DSMB) to oversee the activities of our research trial in order to ensure the safety of participants, the validity of our findings, and the need for further data collection. We propose a DSMB membership that may include a statistician, an expert in diabetes prevention program research, and a

healthcare provider with experience and expertise in the care of prediabetes and diabetes. All of these individuals will also have experience and expertise in the conduct of Phase III Clinical Trials Human Subjects Research. The PIs and investigators will interact with the DSMB at the DSMB's discretion, providing them with material to facilitate fulfillment of the functions detailed below. These include:

Data and Safety Monitoring Plan

Contact PD/PI: [name]

1. Review of protocols, informed consent procedures, and safety plans.
2. Monitor the progress of the intervention, i.e. participant recruitment and retention, risk/benefit ratio for participants, adherence to timetable, and quality of data.
3. Evaluation of the impact of new treatment developments on the risk/benefit ratio of our study.

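### The analysis is labelled intention-to-treat but excludes randomised men who ask to leave the study; the exception is narrow, and the attendance outcomes of Hypothesis 2 are the most exposed

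*Protocol*

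**What the plan says.** The rule stands in the protocol's Data and Safety Monitoring Plan, under Recruitment Monitoring: "all recruited participants will be included in the analyses on an intention-to-treat basis unless they request to be dropped from the study specifically". The next sentence names three groups that stay in: men who want to end only the intervention, men who cannot be contacted, and men without outcome measures. These "will be included in the analysis for outcome measures that are available".

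Four other places bear on the rule:

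- **Timing** (section 1b): "Random assignment, and final enrollment into the study will occur after telephone screening, and completion of baseline surveys". An enrolled man who later asks to be dropped has therefore already been randomised.
- **Knowledge of arm:** Power-Up is "delivered by men coaches in men-only groups" (opening summary), while the comparator classes are mixed-gender. The consent information in section 2a describes both possibilities, "including that participants will be randomized to either standard NDPP or" Power-Up. The blinding that the protocol mentions concerns interim outcome data: "To preserve investigator blinding of outcomes that may bias their interpretation of data".
- **Size** (Timeline): "We will recruit 300, run 8 intervention cycles of approximately 40 men randomized 1:1 to each arm", which is about 150 men per arm.
- **Outcomes:** for weight, "The primary outcome measure will be percent change in weight at the end of the Core (16 weekly) sessions and at the end of 12" (section 1b; the last figure is in months). Hypothesis 2 compares the proportions of randomised men who attend at least 4 sessions (engagement) and 9 or more (retention).

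**The concern.** An intention-to-treat analysis keeps every randomised man in the arm to which he was assigned. Here a man leaves the analysis because of a request that he makes after assignment and with knowledge of his arm. If such requests differ between arms in number or in the kind of man who makes them, the men left are no longer a randomised comparison.

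The attendance outcomes have most at stake. Whether a man reached 4 or 9 sessions is on record up to the day he asks to leave, so there is no missing value to excuse leaving him out. A man who leaves early would plausibly count as not engaged or not retained. Removing him takes a failure out of the denominator and raises his arm's rate.

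The rule also sits badly with the protocol's own reasoning. Section 2a rejects taking consent at the first session because that would select on attendance and make the arms look alike. Section 1b adds weights from health records so that men who never attend still contribute. Both aim to keep selection on behaviour out of the comparison, and the exception lets some back in.

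**Working it through.** The protocol gives no withdrawal rate, so there is no figure of its own to reproduce. The inputs below are assumptions chosen to show scale.

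**Step 1: what the rule does.** The first sentence includes everyone except men who ask to be dropped. The second keeps three groups for whatever outcomes exist. The contrast implies that a man who asks to leave the study is out of the analysis, even for measures already taken. Nothing elsewhere in the protocol keeps his earlier data or limits the exception to men who revoke consent to use their data.

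**Step 2: Hypothesis 2.** Let p be the true engagement rate among all randomised men in an arm and w the fraction removed, with every removed man not engaged. The engaged count is unchanged and the denominator shrinks by the factor 1 − w, so the observed rate is p / (1 − w). Assume p = 0.50 in both arms, so that the true difference is zero.

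| Removed, arm A vs arm B | Arm A | Arm B | Spurious gap |
|---|---|---|---|
| 5% vs 5% | 0.50/0.95 = 52.6% | 52.6% | 0 |
| 1% vs 3% | 0.50/0.99 = 50.5% | 0.50/0.97 = 51.5% | 1.0 points |
| 5% vs 10% | 52.6% | 0.50/0.90 = 55.6% | 2.9 points |
| 5% vs 15% | 52.6% | 0.50/0.85 = 58.8% | 6.2 points |

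Gaps are taken before rounding. The arm that loses more men looks better: if that is NDPP, the error works against Power-Up; if it is Power-Up, it flatters Power-Up.

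**Step 3: weight.** Let d be the mean percent weight change of excluded men minus that of retained men (positive means less loss). The mean over all men in an arm is the retained mean + w × d, so excluding them shifts that arm's mean by −w × d. With the same d in both arms, the arm difference shifts by (difference in w) × d.

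- 1% vs 3%, d = 3: 0.02 × 3 = 0.06 percentage points.
- 5% vs 10%, d = 3: 0.05 × 3 = 0.15 percentage points.
- 5% vs 15%, d = 1 to 3: 0.10 × 1 to 0.10 × 3 = 0.10 to 0.30 percentage points.
- 5% vs 15%, d = 4: 0.10 × 4 = 0.40 percentage points.

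The shift again favours the arm that loses more men.

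**Step 4: what changes if the exception goes.** With all randomised men kept, w = 0 in both arms and the distortion in Step 2 disappears, because attendance is scored from the record. The shift in Step 3 does not disappear in the same way. A man who leaves before week 16 still has no 16-week or 12-month weight, and his contribution then depends on how missing weights are handled.

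**The case against.** The strongest reply is that the exception is narrow. A man disappointed with his programme would most naturally stop attending, and the next sentence keeps him. A reader might infer that all men who quit are removed from the Hypothesis 2 denominators; the protocol does not say that. Only a man who specifically asks to leave the study is removed. This stands, and it limits the size of the problem.

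A reader might also infer that such a man's baseline weight, transmitted weights and attendance are destroyed. The protocol does not say what becomes of them. It says that he is not included in the analyses, and nowhere that his earlier data are kept. The request could also be read as withdrawal of consent, and the consent pages are not available to settle it. Respect for withdrawal, however, requires setting aside earlier data only if the man revokes their use.

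The sentence opens as a remark on retention in a monitoring section, and a statistical analysis plan may define the analysis sets differently. That lowers confidence that it governs the final analysis. It does not remove the conflict, because the sentence itself states who is included in the analyses.

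On size, the rise from 50% to 55.6% is inflation within one arm. It is tempting to read it as a bias of 5.6 points in the comparison, but with 5% removed in the other arm the bias is 2.9 points. To say that the rule by itself breaks the comparison for weight would also go too far: most of that exposure comes from weights that are missing after a man leaves, whatever the rule.

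**Conclusion.** The point holds in a limited form. The protocol's rule and its intention-to-treat label contradict each other, because randomised men who cannot be blinded to arm are excluded on the strength of a post-randomisation choice. The clear exposure is in Hypothesis 2. Under the assumed inputs, the spurious difference runs from 0 with equal exclusion of similar men, through 1.0 and 2.9 points, to 6.2 points at 5% versus 15%. For weight the assumed inputs give 0.06 to 0.40 percentage points; this is small if requests are few, and correcting the rule recovers only part of it.

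These sizes rest on assumed withdrawal rates, an assumed true rate of 50%, the assumption that every excluded man is not engaged, and assumed gaps in weight change. The direction cannot be predicted from the protocol, since it depends on which arm loses more men. That dissatisfaction with the assigned arm drives the requests is plausible but not documented.

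**What to change.** Delete the exception and state that all randomised men are analysed in their assigned arm. For a man who asks to leave:

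- keep the data collected before the request, unless he expressly revokes their use;
- keep him in both Hypothesis 2 denominators, with attendance as recorded to that date;
- treat later weights as missing under the planned missing-data method.

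Report withdrawals by arm, and check that the consent wording agrees with keeping data already collected.

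The cost is an amendment to one sentence, a check of the consent text, and slightly more missing-data handling for weight.
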